### **Overall survival**

OS is defined as the time from the date of the first dose of study treatment to the date of death due to any cause.

### **Changes in platelet count, hemoglobin and neutrophil count**

Value and changes in platelet count (in the absence of platelet transfusion), hemoglobin (in the absence of RBC transfusion) and neutrophil count (in the absence of G-CSF) will be calculated according to the lab test results entered into CRF.

## **2.7.2 Statistical hypothesis, model, and method of analysis**

### **CR rate at Week 13, Week 52 and yearly after**

The number and percentage of subjects who meet the hematological CR criteria (at Week 13, Week 52 and yearly after respectively) will be presented and 2-sided Exact binomial 95% ([Clopper-Pearson](#)) confidence interval will be reported.

### **Overall response (CR+PR) rate at Week 13, Week 26, Week 52 and yearly after**

The number and percentage of subjects who meet the hematological overall response criteria (at Week 13, Week 26, Week 52 and yearly after respectively) will be presented and 2-sided Exact binomial 95% ([Clopper-Pearson](#)) confidence interval will be reported.

The overall response rate will also be summarized by the above subgroups listed in [section 2.2.1](#) for efficacy.

Hematological response endpoints will be listed based on the investigator assessment and the programmatic derivation.

### **Time to response**

The Kaplan-Meier curve of the time to response and time to complete response will be constructed, and the quartiles of the survival function will be provided along with 95% confidence interval. Kaplan-Meier estimates with 95% confidence intervals every 3 months will be summarized as well.

### **Duration of response**

Kaplan-Meier curve of the duration of response and duration of complete response will be constructed, and the quartiles of the survival function will be provided along with 95% confidence interval. Kaplan-Meier estimates with 95% confidence intervals every 3 months will be summarized as well.

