The standard regimen for treatment naive SAA patients who are ineligible for HSCT upfront, is immunosuppressive therapy (IST) comprising anti-thymocyte globulin (ATG) with Cyclosporin A (CsA). Although hematologic recovery with horse ATG (h-ATG)/CsA was observed in 60% to 70% patients, only a minority (about 10% historically) reached complete response (CR) (Scheinberg 2018, Scheinberg and Young 2012). One quarter to one third of the patients did not respond to h-ATG/CsA, and 30-40% of responders relapse (Scheinberg and Young 2012). Outcomes remain poor for patients who have an insufficient response to IST (Olnes et al 2012, Scheinberg and Young 2012).

In most Asian countries, only rabbit ATG (r-ATG) is available on the market, hence, r-ATG/CsA is recommended first-line treatment for patients with SAA in these countries (Red Blood Cell Disease (Anemia) 2017, Kojima et al 2011). Scheinberg et al 2011 and Marsh et al 2012 have reported that patient outcomes including survival were better with h-ATG compared with r-ATG, but studies from Asia had indicated similar responses to r-ATG and h-ATG in AA patients (Chuncharunee et al 2016, Suzuki et al 2016, Shin et al 2013). Recent real world study in China reported that half of the patients treated with IST of r-ATG/CsA achieved overall responses, with 9.4% achieved CRs (Zhu et al 2019), which is comparable with the findings from clinical studies in Asia that have demonstrated overall response rates of 58–70% (Chuncharunee et al 2016, Mahapatra et al 2015, Ramzan et al 2014). Incomplete responses, relapses, and primary refractoriness limit the success of this therapy. This highlights the unmet need to improve outcome following first-line IST in Asian patients.

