8.3 Efficacy

Efficacy assessments include hematologic results, transfusion data, assessment of relapse and survival.

Hematologic parameters will be assessed at Screening, weekly from Week 1 to Week 8, then every 2 weeks to Week 26 (weekly until stabilization of the dose), then every 4 weeks until the end of eltrombopag treatment (every 2 weeks until stabilization of the dose) and yearly during the post-treatment follow-up (up to Year 3). Hematologic parameters will also be assessed as per the investigator decision to assess the maintenance of the response, relapse or for safety reasons.

Transfusion data will be recorded for any transfusion administered during the 60 days prior to treatment start and until the end of eltrombopag treatment for all participants who discontinue eltrombopag due to non-response at W26, relapse or alternative SAA treatment, and until the completion of study follow up for all the other participants. The date and time, content and number of units of each transfusion will be recorded.

Relapse will be determined according to the definition in this section by investigator and will be recorded into eCRF.

All participants will be followed for survival status every 3 months regardless of treatment discontinuation reason up to Year 3 until study completion, death, lost to follow-up, or withdrawal of consent for survival follow-up. Survival information can be obtained via phone, and information will be documented in the source documents and relevant eCRFs.

Hematologic response assessment will be performed by investigators at Week 13, Week 26, Week 52 and yearly after. At Week 13 and Week 26, responses assessment needs to be confirmed by two serial blood count measurements performed 1-3 weeks apart.

Response is defined as blood counts no longer meeting the standard ("Camitta") criteria (Camitta et al 1975) for severe pancytopenia in SAA, equivalent to 2 of the following values (Scheinberg et al 2009).

- Absolute neutrophil count $\geq 0.5 \times 10^9/L$
- Platelet count $\geq 20 \times 10^9/L$
- Reticulocyte count $\geq 20 \times 10^9/L$

A CR will be defined as (all 3 must be met):

- Absolute neutrophil count $> 1.0 \times 10^9/L$
- Platelet count $> 100 \times 10^9/L$
- Hemoglobin $> 100 \text{ g/L}$

A PR will be defined as blood counts that do not meet criteria for SAA but are not sufficient for a CR.

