### **Duration of response**

Duration of response will be derived as the time from first documented and confirmed response (either CR or PR) until the time of relapse or death whichever occurs first. Both the responses and the relapse will be programmatically derived. Patients who are neither complete nor partial responders will not be included in the analysis of the duration of response.

Duration of complete response will be similarly derived for patients who had a complete response. Patients who are not complete responders will not be included in the analysis of the duration of complete response.

Clinical relapse is considered as the occurrence of any of the following event in a subject who had achieved a hematological response (CR or PR) but has subsequently lost response (not explained by any other independent concomitant medical conditions) in one blood count measurements:

- meeting again the criteria for SAA, equivalent to patients with at least two of the following parameters in peripheral blood.
  - Absolute neutrophil count  $< 0.5 \times 10^9/L$
  - Platelet count  $< 20 \times 10^9/L$
  - Absolute reticulocyte count  $< 20 \times 10^9/L$
- requirement for transfusion again for subjects who had been transfusion independent
- decrease in any of the peripheral blood counts to: absolute neutrophil count  $< 0.5 \times 10^9/L$  or platelets  $< 20 \times 10^9/L$ .

The analysis of duration of response will be based on response assessment which are derived programmatically using laboratory results instead of those reported in the response assessment CRF.

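### In the final analysis, 3-monthly Kaplan-Meier estimates of duration of response will be too high between the yearly blood counts scheduled after eltrombopag; the size depends on how many relapses are dated promptly

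*SAP*

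**What the plan says.** **Analysis.** In the final-analysis SAP (sections 2.7.1 to 2.7.3, Duration of response), duration runs from the first confirmed response to relapse or death. "Both the responses and the relapse will be programmatically derived", and the data source is response assessment "derived programmatically using laboratory results instead of those reported in the response assessment CRF". Relapse is a return to the SAA criteria, a fall in neutrophils or platelets below a threshold, or "requirement for transfusion again for subjects who had been transfusion independent". Section 2.7.2 plans Kaplan-Meier curves and quartiles for duration of response and of complete response, and adds "Kaplan-Meier estimates with 95% confidence intervals every 3 months will be summarized as well". Responders without relapse are censored at their last assessment with a known outcome. Neither section 2.7.3 nor section 5.4.2 mentions interval censoring. Duration of response is not among the analyses that section 2.7 drops from the final report.

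**Data.** Protocol section 8.3 schedules counts every 2 to 4 weeks in the extension while eltrombopag is given, then "yearly during the post-treatment follow-up (up to Year 3". Eltrombopag is supplied to Week 52 at the latest (Protocol section 3). Table 8-1 puts Week 52, Year 2 and Year 3 on Days 365, 729 and 1093. Section 8.3 also allows counts at the investigator's discretion, records dated transfusions to study completion for participants still followed as responders, and has the investigator record relapse in the eCRF.

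**The concern.** Ordinary Kaplan-Meier treats the recorded relapse date as the true one. If a relapse is found only at a yearly count, its recorded date is the visit date. The curve then stays too flat between visits and drops at them, and a 3-monthly table reads values off the flat stretches. Those values look more precise than the schedule allows, and their confidence intervals ignore the uncertainty about when relapse occurred.

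At stake is how durable response looks after eltrombopag stops and while CsA may be tapering. Protocol section 4.5 names duration of response among the expected benefits. Section 1.1 quotes a relapse-free estimate at 1.5 years from the pivotal study, so 18 months is a natural point for comparison. For most responders it falls before the Year 2 count.

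**Working it through.** **1. Schedule.** Day = 7 × week + 1 gives 365, 729 and 1093 for Weeks 52, 104 and 156, matching Table 8-1. The gap between counts is 364 days, or 364/30.4375 = 12.0 months. Protocol section 8 allows ±7 days at Week 52 and ±30 days at Weeks 104 and 156. The widest gaps are (364 + 37)/30.4375 = 13.2 months and (364 + 60)/30.4375 = 13.9 months.

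**2. Time scale.** Duration runs from response, not from Day 1. Suppose response starts between Week 6 (Day 43) and Week 26 (Day 183):

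- Week 52 falls at (365 − 183)/30.4375 = 6.0 to (365 − 43)/30.4375 = 10.6 months of duration.
- Week 104 falls at 17.9 to 22.5 months.
- Week 156 falls at 29.9 to 34.5 months.

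So between 10.6 and 17.9 months, and again between 22.5 and 29.9 months, every such responder is between yearly counts.

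**3. Size.** The plan gives no figure for this endpoint, so the size was simulated with 400,000 responders per scenario. Assumptions: response uniform over Day 43 to Day 183; exponential relapse; counts every 2 weeks to Week 26, every 4 weeks to Day 365, then on Days 729 and 1093; no deaths or dropout. The cumulative relapse proportion p at 30 months after response is set to 30% or 40%. The background figure in Protocol section 1.1, "30-40% of responders relapse", concerns h-ATG/CsA and gives no time, so the 30-month horizon is an assumption made here. The rate is λ = −ln(1 − p)/30 per month and the truth is S(t) = exp(−λt). At 18 months S = 0.70^0.6 = 80.7% or 0.60^0.6 = 73.6%.

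Results at 18 months, by the share of relapses dated promptly:

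| Share dated promptly | p = 30%: shown vs true | p = 40%: shown vs true | Bias (points) |
|---|---|---|---|
| None | 90.5 vs 80.7 | 86.6 vs 73.6 | about 10 to 13 |
| Half | 85.6 vs 80.7 | 80.2 vs 73.6 | about 5 to 7 |
| 80% | 82.7 vs 80.7 | 76.1 vs 73.6 | about 2 to 3 |

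The mean dating delay after Week 52 is about 186 days (6.1 months) with none dated promptly, and 93 days over all relapses if half are exact.

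Other times with p = 30% and none dated promptly, shown against true:

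- 12 months: 90.6 vs 86.7
- 24 months: 78.7 vs 75.2
- 30 months: 78.4 vs 70.0
- 33 months: 67.7 vs 67.5

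The bias is not uniform. It is largest near 18 and 30 months and almost gone by 33 months.

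**4. Other relapse rates.** Protocol section 1.1 gives 80.0% and 54.5% relapse-free at 1.5 years for two groups in Cohort 2 of the pivotal study (h-ATG). With those rates, all responses on Day 92 and none dated promptly, the 18-month values are 89.4% against 80.0% and 74.0% against 54.5%. With response on Day 183 the 18-month bias is nearly zero, because Week 104 then falls at 17.9 months. The largest bias moves to 15 months.

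**5. Duration of complete response.** Section 2.7.3 censors complete responders who neither relapsed nor changed to PR. This implies that a change from CR to PR ends the duration. That change is defined by counts, so transfusion dates do little to date it.

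**The case against.** The strongest reply is that yearly counts are not the only way to find relapse. Renewed transfusion is itself a criterion, with recorded dates. Investigators may order counts to check response or suspected relapse. CsA is prescribed monthly to Year 2, survival contact is 3-monthly, and PNH testing is at least 6-monthly to Year 2. With 80% of relapses dated promptly the 18-month bias is 2-3 points. If there are 20 to 25 responders and 80% are relapse-free (assumed), the 95% half-width is 1.96 × √(0.8 × 0.2/n), about 18 to 16 points. This stands as a limit on the size. It does not remove the problem: unscheduled counts are discretionary, none of these other contacts carries a scheduled count, and CR-to-PR changes largely escape transfusion records.

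Four stronger readings are tempting and are not supported:

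- **Every relapse is dated up to a year late.** Twelve months is roughly the maximum for count-only relapses; the mean is about six.
- **Both SAPs need the change.** The primary analysis is cut off after all participants reach Week 26 or withdraw. The last first visit was on 03-Dec-2021 and only three participants were enrolled by 08-Dec-2020, so at most three could have had a Week 104 count by mid-2022. Non-relapsers are censored at their last assessment.
- **Durability is a main question of the final analysis.** It is one of several descriptive secondary endpoints.
- **Duration of response is biased upward overall.** Relapse is called on one unconfirmed count, which could shorten some durations. The upward direction concerns late dating only.

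**Conclusion.** The concern holds for the final-analysis SAP. Followed as written, it reports 3-monthly Kaplan-Meier values that late dating pushes upward from about 12 to 30 months after response. The direction of this effect follows from the schedule. The size does not, because the documents give neither the relapse rate expected here nor the share dated promptly. Under 30-40% relapse within 2.5 years of response, the 18-month bias runs from about 2-3 points (80% dated promptly) to about 10-13 (none). Duration of complete response probably sits nearer the upper end, if a change to PR counts as an event. Participants who stop eltrombopag early can meet the sparse schedule before Week 52. The primary endpoint is not affected.

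**What to change.** In the final-analysis SAP only, add an interval-censored analysis of duration of response and of complete response (Turnbull estimator, PROC ICLIFETEST). Place a count-based relapse, or a count-based loss of CR, between the last count without it and the first count with it, whether scheduled or unscheduled. Keep exact dates for death and transfusion-defined relapse. Show the result beside the Kaplan-Meier curve, and state that 3-monthly Kaplan-Meier values falling between yearly counts are biased upward.

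Reporting only at Year 2 and Year 3 is not an adequate substitute. Response dates are staggered, so those visits match no single duration, and the 24-month value would still read 78.7% against 75.2%.

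The cost is one extra analysis on data already collected. It gives a step curve with wider intervals, and it cannot restore 3-monthly detail that the counts do not contain.

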### **Transfusion-free interval before Week 13 and Week 26**

Descriptive statistics including mean, SD, median, 25th and 75th percentiles, minimum, and maximum will be summarized for the transfusion-free interval. The same analysis applies to RBC transfusion.

### **Maximum duration of Platelet and RBC transfusion free**

Maximum duration of platelet and RBC transfusion free will be summarized by descriptive statistics including mean, SD, median, 25th and 75th percentiles, minimum, and maximum separately.

### **Proportion of subjects who becomes transfusion independent**

The number and percentage of subjects with platelet or RBC transfusion independence at any time during the study will be presented respectively.

### **Transfusion frequency and amount**

The frequency and the amount of platelets and RBC transfusion in each period will be summarized by descriptive statistics including mean, SD, median, 25th and 75th percentiles, minimum, and maximum.

The number and percentage of subjects with platelet or RBC transfusion decrease and 50% platelet transfusion reduction in each period will be presented.

### **Overall survival**

Kaplan-Meier curve of the OS will be constructed, and the quartiles of the survival function will be provided along with 95% confidence interval. OS rate will be estimated at Week 26, Week 52 and yearly after as well.

### **Changes in platelet count, hemoglobin and neutrophil count**

Values and changes in platelet count (in the absence of platelet transfusion), hemoglobin (in the absence of RBC transfusion) and neutrophil count (in the absence of G-CSF) will be summarized at each visit. Descriptive statistics including mean, SD, median, 25th and 75th percentiles, minimum, and maximum will be summarized for the changes. Median and interquartile range will be plotted.

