This is a non-randomized, open label, single arm, multi-center, Phase II study to evaluate the efficacy and safety of eltrombopag in combination with IST regimen of r-ATG + CsA in East-Asian patients with SAA who have not received prior IST. At least 36 participants will be enrolled from China, Japan, Korea or Taiwan. At least 6 pediatric participants will be recruited in total, with 3 participants from China and 3 from Japan respectively. At least one of the 6 pediatric participants in each age group (6 to 11 years old, and 12 to 17 years old) will be enrolled. For the 30 adult participants, at least 12 participants will be recruited from China to fulfill the requirements for pharmacokinetic (PK) profile.

Figure 3-1 Study design

Eligible participants will be enrolled into the study and will receive eltrombopag (from Day 1 to Week 26) concomitantly with r-ATG (on Days 1-5) and CsA (from Day 1 to Week 26) in the core treatment part.

Efficacy assessments will be performed at Week 13 and Week 26 in the core treatment part of the study.

Participants who are assessed as responders (meeting CR or PR criteria) at Week 26 are eligible to the extension part of the study and continue treatment with eltrombopag and CsA after Week 26.

Study treatment should be discontinued if the participant is not assessed as a responder at Week 26.

During the extension part, eltrombopag treatment will be provided up to Week 52. CsA will be maintained or tapered at the investigator's discretion according to local practice, with a total duration of at least 2 years (18 months after Week 26, see [Section 6.1.5](#)). End of treatment (EOT) assessments will be performed after eltrombopag discontinuation at anytime during the study. After that, safety follow-up visit will be performed 30 days after the discontinuation of eltrombopag, and participants will enter the long-term follow-up part, with yearly efficacy and clonal evolution assessments up to Year 3 (Week 156).

For non-responders at Week 26, and participants who relapse or receive alternative SAA treatment, safety follow-up visit will be performed 30 days after the discontinuation of eltrombopag, and then clonal evolution and survival will continue to be followed up to Year 3 (Week 156).

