Participants who prematurely discontinue eltrombopag will have efficacy assessments at defined time points (Week 13, Week 26, Week 52 and yearly after), unless or until the occurrence of no response at Week 26, relapse or alternative SAA treatment (whichever comes first). Survival and clonal evolution data will be collected for all participants up to Year 3 (Week 156)

4 Rationale

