**Figure 1-1 Study design**

Eligible subjects will be enrolled into the study and will receive eltrombopag (from Day 1 to Week 26) concomitantly with r-ATG (on Days 1-5) and CsA (from Day 1 to Week 26) in the core treatment part.

Efficacy assessments will be performed at Week 13 and Week 26 in the core treatment part of the study.

Participants who are assessed as responders (meeting CR or PR criteria) at Week 26 are eligible to the extension part of the study and continue treatment with eltrombopag and CsA after Week 26.

Study treatment should be discontinued if the participant is not assessed as a responder at Week 26.

During the extension part, eltrombopag treatment will be provided up to Week 52. CsA will be maintained or tapered at the investigator's discretion according to local practice, with a total duration of at least 2 years (18 months after Week 26).

End of treatment assessments will be performed after eltrombopag discontinuation anytime during the study. After that, safety follow-up visit will be performed 30 days after the discontinuation of eltrombopag, and participants will enter the long-term follow-up part, with yearly efficacy and clonal evolution assessments up to Year 3 (Week 156).

For non-responders at Week 26, and participants who relapse or receive alternative SAA treatment, safety follow-up visit will be performed 30 days after the discontinuation of eltrombopag, and then clonal evolution and survival will continue to be followed up to Year 3 (Week 156).

Participants who prematurely discontinue eltrombopag will have efficacy assessments at defined time points (Week 13, Week 26, Week 52 and yearly after), unless or until the occurrence of no response at Week 26, relapse or alternative SAA treatment (whichever comes first). Survival and clonal evolution data will be collected for all participants up to Year 3 (Week 156).

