# 4 Change to protocol specified analyses

Below-listed endpoints were added to further support efficacy analysis beyond protocol.

- Time to response
- Maximum duration of Platelet and RBC transfusion free

- Proportion of subjects with transfusion decrease
- Changes in platelet count, hemoglobin and neutrophil count

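### Blood-count medians pooled past Week 26 mix changing groups of participants, so the plotted curve can step up after Week 26 without any individual improving

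*SAP*

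**What the plan says.** SAP 2.7.2 takes "Values and changes in platelet count (in the absence of platelet transfusion), hemoglobin (in the absence of RBC transfusion) and neutrophil count", the neutrophil count being restricted to values without G-CSF. These "will be summarized at each visit", and "Median and interquartile range will be plotted". The text is the same in the primary-analysis and final-analysis SAPs. Neither sets an end at Week 26, a split by response, a count of contributing participants, or a look-back window for transfusion or G-CSF for this endpoint. SAP 2.7.3 has no missing-data rule for it. SAP Section 4 gives its status: "Below-listed endpoints were added to further support efficacy analysis beyond protocol".

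Follow-up depends on response. Protocol Section 3 states: "Study treatment should be discontinued if the participant is not assessed as a responder at Week 26". SAP 1.1 adds: "Participants who are assessed as responders (meeting CR or PR criteria) at Week 26 are eligible to the extension part of the study". For non-responders, relapsers and those who switch treatment there is a safety visit, "and then clonal evolution and survival will continue to be followed up to Year 3 (Week 156"). Participants who stop eltrombopag early keep efficacy assessments "unless or until the occurrence of no response at Week 26, relapse or alternative SAA treatment (whichever comes first"). Protocol 9.1.1 makes relapse a reason to stop study treatment.

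In Protocol Table 8-1, haematology at Years 2 and 3 has a plain mark. Response assessment and transfusion recording there carry footnote 2, which excludes participants who stopped for non-response, relapse or alternative treatment. Protocol 6.2.1 and 8.3 end transfusion recording for those participants when eltrombopag ends.

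**The concern.** A median plotted over visits is naturally read as the course of one group. Here the group changes in two ways that depend on outcome. Up to Week 26, values taken under transfusion or G-CSF are left out, and these come mainly from participants doing badly. After Week 26, non-responders have no extension visits and relapsers drop out as they fail. At Years 2 and 3 former non-responders may return, possibly after other treatment, and there is no record from which to confirm that their counts were free of transfusion.

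The analysis was added to support efficacy. A step up after Week 26, or a high plateau during the extension, could be taken as further recovery or as maintained response when part or all of it reflects who is still measured.

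**Working it through.** **1. Who can contribute**

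| Visits | Contributors | Source |
|---|---|---|
| Baseline to Week 26 | All in follow-up, less values under transfusion or G-CSF | SAP 2.7.2; Protocol Table 8-1 |
| Weeks 28 to 52 | Week 26 responders, less those who relapse or switch | Protocol 3 and 9.1.1; SAP 1.1 |
| Years 2 and 3 | Responders still followed, plus possibly non-responders with transfusion status unknown | Protocol 6.2.1, 8.3, Table 8-1 |

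Week 26 itself still includes the non-responders, so the change falls after that visit. SAP 2.1 (primary analysis) uses all data up to the cut-off, so early enrollees can already have extension visits in the primary analysis.

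**2. The plan's own figures**

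The plan gives no figure for this analysis. Its sample-size table reproduces: 16/36 = 44.4% (27.9, 61.9), maximum half-width 17.08%. This point does not depend on it.

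**3. Inputs for an illustration in platelets**

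- N = 36 (SAP 3.1).
- Response rate r = 57.1%, which is 4 of 7 in the Japanese r-ATG study (Protocol 4.5). It is varied over 50%, 70% and 85%; Protocol 1.1 quotes 58 to 70% for Asian r-ATG studies.
- Assumed, not in the documents: lognormal counts, log-SD 0.6, and responder/non-responder medians of 80/15 or 60/25 x10^9/L.
- t = share of non-responder values excluded as transfused: 0, 0.5, 0.9 or 1.
- Every individual count is held constant across Week 26.

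**4. Formula**

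Among values kept at Week 26 the responder share is w = r / [r + (1 - r)(1 - t)]. The plotted median m solves

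w x Phi[(ln m - ln 80)/0.6] + (1 - w) x Phi[(ln m - ln 15)/0.6] = 0.5.

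At the next visit only responders remain, so the median is 80. Step = 80 - m. Lift from exclusion = m - (m at t = 0).

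Example, t = 0.5: w = 0.571/(0.571 + 0.429 x 0.5) = 0.727. At m = 60 the left side is 0.727 x 0.316 + 0.273 x 0.990 = 0.50, so the step is 20.

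**5. Results, r = 57.1%, medians 80/15**

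| Non-responder values excluded | n at Week 26 | Week 26 median | n after | Median after | Step | Lift already present at Week 26 |
|---|---|---|---|---|---|---|
| None | 36.0 | 43 | 20.6 | 80 | 37 | 0 |
| Half | 28.3 | 60 | 20.6 | 80 | 20 | 17 |
| 90% | 22.1 | 76 | 20.6 | 80 | 4 | 32 |
| All | 20.6 | 80 | 20.6 | 80 | 0 | 37 |

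Each entry is rounded separately. Step and lift together always come to about 37 (80 - 43). More exclusion makes the step smaller and the Week 26 distortion larger.

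**6. Sensitivity (none / half / 90% / all excluded)**

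| Medians | Response | Step | Lift |
|---|---|---|---|
| 80/15 | 50% | 45 / 26 / 6 / 0 | 0 / 20 / 40 / 45 |
| 80/15 | 70% | 22 / 12 / 3 / 0 | 0 / 11 / 20 / 22 |
| 80/15 | 85% | 10 / 5 / 1 / 0 | 0 / 5 / 9 / 10 |
| 60/25 | 57.1% | 18 / 11 / 3 / 0 | 0 / 7 / 16 / 18 |

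**The case against.** The strongest defence is that untransfused counts match the response criteria in SAP 2.5.1, that this is an added descriptive summary in a study with no formal testing, and that the SAP already covers the gaps. SAP 2.8.3 summarises the same three counts regardless of transfusion or G-CSF. Response rates count non-evaluable participants as non-responders. Maintenance has its own Kaplan-Meier analysis of duration of response.

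Much of this stands. Using untransfused values is a legitimate choice, and the low weight of the analysis limits the harm. The SAP 2.8.3 summary offsets the transfusion selection up to Week 26. It does not cure the later problem: it covers the on-treatment period only (SAP 2.8), so it loses the same non-responders after Week 26, and no median plot is stated for it.

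Several stronger readings are tempting but not supported:

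- That the whole upward trend is an artefact. Participants enter meeting the SAA count criteria; if no count changed there would be no responders to plot.
- That a step must occur. It falls to zero if all non-responder values are already excluded. Non-response does not require every lineage to be low, haemoglobin is not among the partial-response criteria, and only G-CSF removes neutrophil values.
- That non-responders leave the schedule. They keep end-of-treatment, safety and yearly marrow visits.
- That participants with a transfused baseline are lost from change scores. Protocol 8.2 and SAP 2.1.1 define baseline differently, but neither states that exclusion.
- That the final analysis will show the same step. The final-analysis SAP 2.7 says Week 13 and Week 26 changes will not be reproduced. The selected later visits would then appear without their Week 26 reference.

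**Conclusion.** The concern holds in limited form. Points after Week 26 describe a group selected on response, the whole-group points up to Week 26 describe values selected on not needing support, and nothing in the planned display shows either. At 57.1% response with medians 80/15, the post-Week 26 step with no individual change lies between 0 and 37 x10^9/L, and the lift at Week 26 lies between 37 and 0 in the opposite order. With 60/25 both ranges narrow to 0 to 18.

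The mechanism follows from the documents. The sizes rest on assumed medians, spread and exclusion shares, and cover platelets only. The direction needs responders to have higher counts in the lineage plotted. Severity is low to moderate: the primary endpoint and the protocol's secondary endpoints are unaffected.

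**What to change.** In SAP 2.7.2, replace the single pooled display with two fixed groups:

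- The whole FAS, from baseline to Week 26 only.
- Week 26 responders, from baseline to Year 3, labelled as such and excluding counts after alternative SAA treatment.

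At each visit print the number contributing and the number excluded for transfusion or G-CSF, and state the look-back used. Up to Week 26, show the all-values median from SAP 2.8.3 beside the untransfused one. In the final analysis, keep the Week 26 values in the responder panel as its reference.

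Worst-rank imputation should not be required. The median could not be plotted when more than half are supported, the planned mean and SD would be undefined, and G-CSF use need not mean the lowest neutrophil count.

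The data needed are already collected. The cost is SAP wording, one extra panel, and a whole-group curve that looks less steep. Regrouping cannot recover counts that relapsers no longer provide, so maintenance should still be read from the duration-of-response analysis.
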